#### 6.3.2 Blinding

This is an open-label study. Information about the drug for the treatment of acute gout attacks is unblinded to patients and investigators. In this study, there are subjective criteria for assessing the efficacy of study therapy, and information about the drug taken may affect the evaluation of the efficacy of the investigational product by the investigator and the patient. However, since this study is exploratory and is conducted with the aim of assessing the possibility of treating patients with an acute gout attack with RPH-104 in principle, the open-label design of the study is considered acceptable. The efficacy data from this study are not intended to be used to determine the sample size in blind studies.

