# 8.1 Early withdrawal from the study

The withdrawal criteria are:

- Withdrawal of informed consent.
- Patient's death.
- Patient's pregnancy.
- A significant protocol deviation, which, in the opinion of the Investigator, and upon agreement with the Sponsor, could result in an incorrect interpretation of the study results.

The use of a rescue medication, prohibited drugs, and missing certain procedures or individual visits are generally not the reasons for discontinuation of the patient from the study. In these cases, the patient should be offered to continue the visits and examinations in accordance with the clinical study protocol.

The Investigator should make all reasonable efforts to determine the reason of the patient's withdrawal from the study. The date and reason for the patient's early withdrawal from the study had to be clearly described in the CRF for any patient who received at least one dose of the investigational product.

If a patient is withdrawn from the study due to pregnancy, the Investigator provides the Sponsor with information concerning the pregnancy outcome (see Section 12.7).

Regardless of the reasons for early withdrawal from the study, no replacement of withdrawn patients is to be made.

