### 10 CLINICAL EVALUATION PLAN AND STUDY VISITS

The time frames established by the Study Protocol should be observed for all the visits described below.

The study site personnel should make all efforts to conduct the assigned schedule of procedures and visits exactly as required by the Study Protocol.

All deviations from the study flow chart and procedures scheduled for the visits should be documented in the CRF.

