# Screening day (screening procedures and baseline assessments)

The patients are invited to participate in the study and are given a copy of the Patient Information Sheet with Informed Consent Form for review and making a decision about their participation. The patient's written informed consent to participation in the study must be obtained before any procedures scheduled in this study, including the screening procedures, are carried out.

Patients who have read the Patient Information Sheet and signed the Informed Consent Form will be assigned numbers by the online randomization system in the order in which they visit the study site during the screening visit procedures. The number for each patient will consist of two parts: the first two digits will indicate the site number, the next three digits will indicate the assigned serial number of the patient. The individual patient number is retained for subsequent randomization.

Example of patient number assignment: At site 1, the first patient who signs the informed consent form will be assigned number 01001, which will be retained through randomization. The second patient who signs the informed consent form is assigned number 01002. Let us assume that the second patient was not randomized. Then he drops out of the study with number 01002. The third patient receives number 01003. The number assigned to the patient will be indicated on all study documents and in the source documentation.

If a patient is withdrawn from the study during the screening period (an exclusion criterion identified, patient's refusal to participate, etc.), the reason for withdrawal should be specified in the screening log. In this case, the patient can take part in the study again.

After signing the informed consent form for participation in the clinical study, the following procedures are performed at screening:

• Confirmation of the diagnosis, documenting the information about the primary disease;

NOTE. The diagnosis of gout can be made at a visit to the study site during a current gout attack based on the American College of Rheumatology (ACR) and European League Against Rheumatism (EULAR) criteria of 2015 with the total score of 8. Uric acid level as the diagnostic criterion can be determined earlier, regardless of when. The highest uric acid levels ever measured must be used.

- Collection of demographic data, medical history, information about previous and concomitant therapy;

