### Day 1 (randomization and initiation of therapy)

Patients meeting the eligibility criteria are randomized to receive therapy with either of the investigational products, RPH-104 or Voltaren® (diclofenac).

After randomization, the patients undergo the following procedures:

- Blood collection for the following tests (only for patients randomized to the RPH-104 group, prior to drug administration):
  - o Baseline blood sample to study the RPH-104 pharmacokinetics (central laboratory);
  - Baseline blood sample to study anti-RPH-104 antibody levels (central laboratory);
- Subcutaneous injection of RPH-104 (only for patients randomized to RPH-104 groups);

NOTE. The time of administration of RPH-104 is recorded in the source documentation and CRF. Sampling time for subsequent blood samples to assess pharmacokinetics, pain intensity in the assessed joint, and patient global assessment of efficacy are counted from this time. The acceptable time intervals for these procedures are indicated in the Study Procedure Table (see Section 3).

Evaluation of pain intensity in the assessed joint and patient global assessment of efficacy are performed before pharmacokinetic blood sampling in accordance with the pre-specified time intervals for these procedures.

• Dispensing Voltaren® (diclofenac) and Ortanol® (omeprazole) to the patient in an amount sufficient for use until the end of the treatment period (only for patients randomized to the Voltaren® (diclofenac) group);

*NOTE.* Subcutaneous injection of RPH-104 or the first dose of Voltaren® (diclofenac) must be given within 30 minutes after randomization.

By the decision of the investigator, after the use of the investigational products, patients can be hospitalized and remain under observation in the hospital or continue to participate in the study on an outpatient basis.

After administration of the investigational products, outpatients remain under the supervision of the investigator for at least 3 hours, after which they are allowed to leave the study site. These patients should return to the study site for all analyses and assessments in accordance with the study procedure schedule (Table 3.1).

- Dispensing questionnaires to the patient to record the following:
  - Pain intensity in the assessed joint according to VAS (at 15, 30, 45 minutes, 1, 1.5 h after the use of the investigational product);

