#### **13.1.1** Analysis populations

#### Efficacy population

To assess the treatment efficacy, the population of all randomized patients who received at least one dose of the investigational product and who had at least one VAS measurement of the patient's pain intensity in the assessed joint after the start of the investigational product therapy will be used.

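### The open-label arm is known before the first dose, yet undosed randomised patients leave the efficacy population and only dosed patients expressly need a withdrawal reason in the CRF, so exclusion can depend on arm

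*Combined protocol and SAP*

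**What the plan says.** Section 6.3.2 states: "Information about the drug for the treatment of acute gout attacks is unblinded to patients and investigators". Section 6.3.1 has the investigator randomise through the IWRS and record the assigned group in the source documents. Under section 10.2 (Day 1), the injection or the first diclofenac tablet "must be given within 30 minutes after randomization".

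Section 13.1.1 defines the efficacy population as "all randomized patients who received at least one dose of the investigational product and who had at least one VAS measurement" of pain in the assessed joint after the start of therapy. The safety, pharmacokinetic and pharmacodynamic populations also require that the product was received. No set of all randomised patients is defined.

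On withdrawals, section 8.1 gives a general duty: "The Investigator should make all reasonable efforts to determine the reason of the patient's withdrawal from the study". The recording rule that follows is narrower: the date and reason "had to be clearly described in the CRF for any patient who received at least one dose of the investigational product". Section 8.1 also says that "no replacement of withdrawn patients is to be made", and exclusion criterion 33 bars re-entry after randomisation. For the screening period, section 10.2 says "the reason for withdrawal should be specified in the screening log"; nothing equivalent covers the interval between randomisation and first dose. Section 10 adds a general rule: "All deviations from the study flow chart and procedures scheduled for the visits should be documented in the CRF".

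For missing efficacy data, section 13.1.6 prescribes baseline observation carried forward (BOCF). The baseline VAS is taken within 1 hour before randomisation (section 10.2).

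**The concern.** Leaving never-dosed patients out of an efficacy analysis is usually harmless when the decision to start cannot depend on the assigned treatment. Here it can. Patient and investigator know the arm for up to 30 minutes before the first dose, and the arms differ visibly: one day of injection, or 12 days of an oral NSAID. Exclusion criteria 1-3 of section 7.3 admit patients who have already used an NSAID, including diclofenac, once a washout of hours has passed. Such a patient, still at 50 mm or more, might accept an injection but decline diclofenac.

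At stake are the contrasts of each RPH-104 group with diclofenac in sections 13.5.2 and 13.5.3. If refusals differ by arm, these compare patients willing to start each treatment, not the groups as randomised. With 14 controls, each missing patient is 1/14 = 7.1% of the arm. No section requires the report to count such patients by arm.

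**Working it through.** **The plan's own figures (section 13.1.2).** Inputs: SD 26 mm, 14 per group, two-sided 5%.

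- Total: 15 + 4 × 14 + 14 = 85, as stated.
- Full width of a 95% CI for one group mean: 2 × t(0.975, 13) × 26/√14 = 30.0 mm. The stated accuracy of 30 mm is thus a full width.
- Pairwise standard error: 26 × √(2/14) = 9.83 mm.
- Smallest significant observed difference: t(0.975, 26) × 9.83 = 20.2 mm, which matches the stated 20 mm.

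These figures reproduce, and this point contradicts none of them. The plan states no allowance for undosed patients.

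**Two diclofenac patients side by side.**

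- Patient A takes one tablet, gives the 15-minute VAS and withdraws. A is in the efficacy population (13.1.1), enters the 72 h analysis at the baseline value, that is zero change (13.1.6), and must have a withdrawal reason in the CRF (8.1).
- Patient B learns the arm and declines a few minutes earlier. B is in no analysis population, and the CRF reason rule of 8.1 does not name B. What remains is the source record of the assignment (6.3.1), the general effort to find the reason (8.1) and a documented deviation (10).

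The two are treated differently although both left early and neither has a 72 h value.

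**Shift caused by exclusion.** Let k of the 14 patients in one arm decline, and let d be the difference between the mean 72 h change of dosed patients and the mean change the decliners would have had. The mean over all 14 differs from the mean over the dosed by k × d/14. The documents give neither k nor d; both are assumed.

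| k | d = 10 mm | d = 20 mm | d = 30 mm |
|---|---|---|---|
| 1 | 0.7 | 1.4 | 2.1 |
| 2 | 1.4 | 2.9 | 4.3 |

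The largest entry is 4.3/9.83 = 0.44 of a pairwise standard error and 4.3/20 = 21% of the stated difference.

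**Loss of precision.** With 13 or 12 analysed in one arm, the full CI width for that arm is 31.4 or 33.0 mm instead of 30.0. The smallest significant difference against an arm of 14 is 20.6 or 21.1 mm instead of 20.2.

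**What a zero-change sensitivity run would show.** If dosed patients fall by an assumed mean of m = 30-50 mm and decliners are set to zero change, the arm mean moves by k × m/14: 2.1-3.6 mm for one patient and 4.3-7.1 mm for two. This is the expected distance between the main and sensitivity results. It does not estimate exclusion bias, because decliners' true change need not be zero.

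**The case against.** A colleague could say that this is a small gap in an exploratory study. The first tablet is taken at the site, patients consent after being told about methods and risks, and those with NSAID intolerance are excluded, so few are likely to refuse within 30 minutes. The main output for the primary endpoint is descriptive statistics and a CI per group; the contrasts with diclofenac are supplemental, and section 13.7 plans no formal hypothesis testing. Section 6.3.2 accepts the open-label design openly. Further detail is left to a separate SAP (13.1.7), which may contain a disposition table. Non-replacement is not a fault either, since replacing decliners would add selection.

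Most of this stands and limits the size of the problem. It does not close the gap. Section 6.3.2 accepts that knowledge of the drug may influence efficacy ratings; it does not address refusal before dosing. Supplemental contrasts are still planned results. The deviation rule and the duty of reasonable effort leave a trace, but neither requires the reason to be written in the CRF or a count by arm to be reported.

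Some stronger inferences are tempting and not supported:

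- That a decliner would vanish from the record. The source record of the assignment and the deviation rule say otherwise.
- That the 2.1-7.1 mm range is the bias. It is the effect of imputing zero change.
- That the shift should be judged against the 7 controls of one period. Section 13.5.2 plans no comparison by period.
- That the main analysis must become all-randomised with BOCF. A gout attack resolves over time (section 4.6 gives up to 14 days), so zero change at 72 h may be pessimistic for a decliner. If refusals fall on diclofenac, that would make the control look worse.

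**Conclusion.** The point holds as a gap in the analysis sets and in record-keeping. The arm is known before dosing, every analysis set requires the product, and the express date-and-reason rule covers only dosed patients, so exclusion from the diclofenac contrasts can depend on arm. The documents do not show that it has happened, and they give no refusal rate.

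Under the assumptions of 1-2 decliners among 14 and a 10-30 mm difference in mean change, the arm mean shifts by about 0.7-4.3 mm, less than half of the 9.8 mm pairwise standard error. That would not by itself overturn a 20 mm difference, but it is large enough to report. If nobody declined, the shift is zero and one line in the report settles the matter.

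**What to change.** - **13.1.1 and 13.5.2:** keep the dosed-with-VAS set as the main efficacy population. Add a sensitivity analysis of the primary ANCOVA in all randomised patients by assigned arm. Where no 72 h value exists, apply the BOCF rule of 13.1.6 to the baseline VAS taken before randomisation.
- **8.1:** extend the CRF record of date and reason of withdrawal to every randomised patient, dosed or not.
- **Report:** tabulate randomised-but-never-dosed patients by arm, including for the 47-patient interim analysis, whose report may become final (section 4).

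The analysis and reporting parts can still be specified, because the separate SAP is to be approved before the interim data lock (13.1.7). For the 47 patients who have completed participation, the new recording rule comes too late; their count can be taken from the IWRS, source and deviation records.

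The cost is one extra model run, one table and a change of CRF wording. The sensitivity result is a check and not a bound: a decliner who would have worsened, or improved more than the arm mean, lies outside both results.

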# 8.2 Premature termination of the study at an individual study site and premature termination of the study in general

The sponsor reserves the right to terminate the study at an individual study site or at all sites at any time due to reasons of medical and/or administrative nature.

In case of premature study termination, the Investigator should, regardless of the reason for this decision, immediately notify all patients and ensure their follow-up and further treatment. The sponsoring company will notify in writing the Investigator and regulatory authorities about the termination of the study, indicating the reasons for this decision.

In case of premature termination of the study, the Investigator should, if possible, conduct the procedures and evaluations scheduled for the follow-up visit for early withdrawal in all patients who have not completed their participation in the study by this time (see Section 10.3).

CONFIDENTIAL P. 41 of 84

# 9 PATIENT TREATMENT

# 9.1 Description of investigational products and concomitant therapy

Investigational product provided by the Sponsor

RPH-104 solution for subcutaneous injection, 40 mg/mL is provided by the Sponsor of the study.

Name	RPH-104/L04018
Dosage form	RPH-104 solution for subcutaneous injection, 40 mg/ml, 2 mL
Active substance	RPH-104/L04018
Excipients	Sucrose, Polyethylene glycol (PEG) 3350, sodium chloride, L-histidine
Appearance	A clear or slightly opalescent solution
Packaging	4 mL glass vial with RPH-104 solution for subcutaneous injection, 2 mL
Manufacturer	Branch of R-Pharm JSC, Yaroslavl Factory of Finished Dosage Forms, [name] phone/[contact].

# Reference product

Voltaren® (diclofenac) enteric-coated tablets, 25 and 50 mg is provided by the study Sponsor.

Marketing authorization holder (owner): Novartis Pharma Limited, Switzerland.

Trade name: Voltaren® tablets 25 mg and 50 mg

Name	Voltaren®
INN	diclofenac
Dosage form	Enteric coated tablets 25 mg and 50 mg
Active substance	diclofenac sodium
Excipients	anhydrous colloidal silicon dioxide, microcrystalline cellulose, lactose monohydrate, magnesium stearate, corn starch, povidone K30, sodium carboxymethyl starch
Coating composition:	For 25 mg: hypromellose, macrogolglycerol hydroxystearate, dye iron oxide yellow, talc, titanium dioxide
	For 50 mg: hypromellose, macrogolglycerol hydroxystearate, dye iron oxide yellow, dye iron oxide red, talc, titanium dioxide
Enteric coating composition	copolymer of methacrylic acid and ethyl acrylate (1:1), macrogol 8000, silicone antifoam emulsion SE2, talc
Colored coating composition	For 25 mg: hypromellose, macrogolglycerol hydroxystearate, dye iron oxide yellow, talc, titanium dioxide
	For 50 mg: hypromellose, macrogolglycerol hydroxystearate, dye iron oxide yellow, dye iron oxide red, talc, titanium dioxide
Appearance	For 25 mg: yellow, round, biconvex, bevelled-edged enteric-coated tablets embedded with "CG" on one side of the tablet and "BZ" on the other
	For 50 mg: light brown, round, biconvex, bevelled-edged enteric-coated tablets embedded with "CG" on one side of the tablet and "GT" on the other
Packaging	For 25 mg and 50 mg:
	2 10-tablet blisters per carton

CONFIDENTIAL P. 42 of 84

	3 10-tablet blisters per carton
Manufacturer	NOVARTIS Saglik Gida ve Tarim Urunlery Sanayi ve Ticaret, A.S., Turkey

Concomitant drug for patients receiving Voltaren® (diclofenac)

Ortanol® (omeprazole) 20 mg capsule is provided by the study sponsor.

Marketing authorization holder (owner): Sandoz dd, Slovenia.

Trade name: Ortanol®, capsules, 20 mg

Name	Ortanol®
INN	omeprazole
Dosage form	Capsule
Active substance	omeprazole
Excipients	Low-substituted hydroxypropyl cellulose, MCC, anhydrous lactose, croscarmellose sodium, povidone, polysorbate 80, hypromellose phthalate, dibutyl sebacate, talc
Capsule coating	Hypromellose, carrageenan, potassium chloride, titanium dioxide, iron (III) oxide yellow (for 40 mg), iron (III) oxide red (for 40 mg), water, printing ink: iron (III) oxide black (E172), shellac, anhydrous ethanol, anhydrous isopropanol, propylene glycol, butanol, ammonium hydroxide, potassium hydroxide, purified water
Appearance	Hard capsules No. 2, white body and cap inscribed with "OME 20" in black ink on both parts of the capsule
Packaging	7 capsules per blister, 4 blisters per carton
Manufacturer	Lek Pharmaceuticals dd, Slovenia

## 9.2 Packaging and labelling

Investigational product RPH-104 solution for subcutaneous injection, 40 mg/mL, 2 mL will be supplied in 4 mL vials. 1 vial per carton.

Voltaren® (diclofenac) will be supplied as 25 and 50 mg film-coated tablets in the manufacturer's original packaging.

Ortanol® (omeprazole) will be supplied in the form of 20 mg capsules in the manufacturer's original packaging.

The investigational product RPH-104, Voltaren® (diclofenac), Ortanol® (omeprazole) and Kenalog® (triamcinolone) are labeled in accordance with the requirements of the Russian legislation.

# 9.3 Storage conditions

Storage of products used in this study is the responsibility of an authorized employee or pharmacist of the study site. RPH-104 must be stored under the following conditions:

• At 2°C to 8°C. Do not freeze.

Voltaren® (diclofenac) and Ortanol® (omeprazole) should be stored under the following conditions:

• In a dry, dark place, below 25 °C.

CONFIDENTIAL P. 43 of 84

Kenalog® (triamcinolone) must be stored under the following conditions:

• In a dark place, at 8°C to 25°C. Do not freeze.

The drugs must be stored in commercial packaging in a secured place with limited access. An authorized employee or pharmacist of the study site should monitor the temperature regime in the refrigerator in which the drugs are stored, and record the temperature on weekdays, taking into account the minimum and maximum temperatures from the previous measurement.

# 9.4 Accounting and destruction of investigational products and concomitant therapy

The authorized employee or pharmacist of the study site is responsible for the receipt of all study drugs at the study site. Upon delivery of a product lot to the study site, the authorized employee examines the cargo and fills out the reception confirmation form. A copy of this form should be retained at the study site, and the original should be sent to the Sponsor or an organization designated by the Sponsor.

During the study, the investigational products RPH-104, Voltaren® (diclofenac), Kenalog® (triamcinolone) and the concomitant drug Ortanol® (omeprazole) should be accounted for. The patient must return all Voltaren® (diclofenac), Kenalog® (triamcinolone) and Ortanol® (omeprazole) issued to the patient and unused and all packages from used Voltaren® (diclofenac), Kenalog® (triamcinolone) and Ortanol® (omeprazole) to the investigator. Returned Voltaren® (diclofenac), Kenalog® (triamcinolone) and Ortanol® (omeprazole) are accountable. Voltaren® (diclofenac), Kenalog® (triamcinolone) and Ortanol® (omeprazole) returned by the patient cannot be re-dispensed.

Returned unused Voltaren® (diclofenac), Kenalog® (triamcinolone) and Ortanol® (omeprazole) and used Voltaren® (diclofenac), Kenalog® (triamcinolone) and Ortanol® (omeprazole) packages must be retained at the Study Center until specifically instructed by the Sponsor.

The procedure for destruction of the investigational products will be determined by the Study Sponsor.

